6.3.1 Pulmonary Adverse Events

Pulmonary AEs have been observed following treatment with Nivolumab. The majority of cases reported were Grade 1 or 2, and subjects presented with either asymptomatic radiographic changes (e.g., focal ground glass opacities and patchy infiltrates) or with symptoms of dyspnea, cough, or fever. Subjects with reported Grade 3 or 4 pulmonary AEs were noted to have more severe symptoms, more extensive radiographic findings, and hypoxia. At this time, no other underlying risk factor, including prior radiotherapy, presence of lung metastases, or underlying pulmonary medical history, has yet to be identified. Asymptomatic subjects were typically managed with dose delay. Subjects with Grade 2 pneumonitis were managed with dose delay, treated with corticosteroids, and had resolution of pneumonitis within days to weeks. In cases where Nivolumab treatment was restarted, recurrence of pneumonitis was infrequently reported across the Nivolumab program. Subjects with more severe cases of pneumonitis can be difficult to treat. In a few cases, subjects who did not initially respond to corticosteroids were administered anti-tumor necrosis factor therapy (infliximab) and/or cyclophosphamide. In some of these cases, pneumonitis began to resolve following the use of these additional therapies.

Early recognition and treatment of pneumonitis is critical to its management. Subjects should be advised to seek medical evaluation promptly if they develop new-onset dyspnea, cough, or fever or if they have worsening of these baseline symptoms. For symptomatic Nivolumab-related pneumonitis, the principal treatment is corticosteroids. All subjects with Grade 3-4 pneumonitis should discontinue Nivolumab and initiate treatment with high doses of corticosteroids. Consultation with a sponsor-investigator should be sought for all suspected cases of pneumonitis.

6.3.2 Gastrointestinal Adverse Events

Gastrointestinal AEs have been observed following treatment with Nivolumab. Most cases of diarrhea were of low grade (Grade 1-2). Colitis occurred less frequently than diarrhea. High-grade cases of diarrhea and colitis were managed with corticosteroids and, in all cases, the events resolved. Early recognition and treatment of diarrhea and colitis are critical to their management. Subjects should be advised to seek medical evaluation if they develop new-onset diarrhea, blood in stool, or severe abdominal pain or if they have worsening of baseline diarrhea. As GI symptoms are common in subjects with cancer, it is important that an evaluation/work-up distinguishes between non-drug-related causes (e.g., infection or progression of disease) and a possible drug-related AE as the management can be quite different. The principal treatment for high-grade GI AEs is corticosteroids. Caution should be taken in the use of narcotics in subjects with diarrhea, colitis, or abdominal pain as pain medicines may mask the signs of colonic perforation. Consultation with a sponsor-investigator should be sought for all moderate- and high-grade cases of GI AEs.

6.3.3 Hepatic Adverse Events

Hepatic AEs, including elevated liver function tests (LFTs) and, infrequently, drug induced liver injury (DILI), have been observed following treatment with Nivolumab. Most cases were of low or moderate grade. Higher-grade hepatic AEs, including DILI, were managed with corticosteroids (with or without mycophenolate mofetil) and, in almost all cases, the events resolved. Early recognition and treatment of elevated LFTs and DILI are critical to their management. Subjects should be advised to seek medical evaluation if they notice jaundice (yellow appearance of skin or sclera) or if they develop bruising, bleeding, or right-sided abdominal pain. Physicians should monitor LFTs prior to each Nivolumab treatment. As LFT abnormalities are common in subjects with cancer, it is important that an evaluation/work-up distinguishes between non-drug-related causes (e.g., infection, progression of disease, concomitant medications, or alcohol) and a possible drug-related AE as the management can be quite different. The principal treatment for high-grade hepatic AEs is corticosteroids. Consultation with a sponsor-investigator should be sought for all moderate- and high-grade hepatic AEs.

6.3.4 Endocrinopathies

Endocrinopathies have been observed following treatment with Nivolumab. Most cases were of low or moderate grade. The events have typically been identified through either routine periodic monitoring of specific laboratories (e.g., TSH) or as part of a work-up for associated symptoms (e.g., fatigue). Events may occur within weeks of beginning treatment, but also have been noted to occur after many months (while still on treatment). More than 1 endocrine organ may be involved (e.g., hypophysitis [pituitary inflammation] may need to be evaluated at the time adrenal insufficiency or thyroid disorder is suspected). Moderate- to high-grade cases were

managed with hormone replacement therapy and, in some cases, with the addition of corticosteroids. In some cases, Nivolumab treatment was held until adequate hormone replacement was provided. Early recognition and treatment of endocrinopathies are critical to its management. Subjects should be advised to seek medical evaluation if they notice new-onset fatigue, lightheadedness, or difficulty with vision or if baseline fatigue worsens. As fatigue is common in subjects with cancer, it is important that an evaluation/work-up distinguishes between non-drug-related causes (e.g., progression of disease, anemia, concomitant medications, or depression) and a possible drug-related AE as the management can be quite different. The principal management of endocrinopathies is hormone replacement therapy. For subjects with moderate- or high-grade events, corticosteroids may also be used. Consultation with a sponsor-investigator should be sought for all moderate- and high-grade cases of endocrinopathies.

6.3.5 Skin Adverse Events

Rash and pruritus were the most common skin AEs observed following treatment with Nivolumab. The rash was typically focal with a maculopapular appearance occurring on the trunk, back, or extremities. Most cases have been of low or moderate grade. In some cases, rash and pruritus resolved without intervention. Topical corticosteroids have been used for some cases of rash. Anti-histamines have been used for some cases of pruritus. More severe cases responded to systemic corticosteroids. Subjects should be advised to seek medical evaluation if they notice new-onset rash. Early consultation with a dermatology specialist and a biopsy should be considered if there is uncertainty as to the cause of the rash, or if there is any unusual appearance or clinical feature associated with it. Other drugs that may cause rash should be considered in the differential and, if possible, discontinued. In addition, careful evaluation of potential benefit-risk is necessary when considering the use of Nivolumab in a patient who has previously experienced a severe or life-threatening skin adverse reaction on a prior immune-stimulating therapy. The principal treatment for skin AEs, such as rash and pruritus, consists of symptomatic management. Topical corticosteroids can be used for low- to moderate-grade focal rash. Systemic corticosteroids should be used for diffuse and high-grade rash. Consultation with a Sponsor's medical monitor should be sought for all moderate- and high-grade cases of skin AEs. Rare cases of Stevens-Johnson syndrome (SJS) and toxic epidermal necrolysis (TEN), some with fatal outcome, have been observed. If symptoms or signs of SJS or TEN appear, Nivolumab should be withheld and the patient referred for specialized care for assessment and treatment. If the patient has confirmed SJS or TEN, permanent discontinuation of Nivolumab is recommended.

6.3.6 Renal Adverse Events

Elevated creatinine and biopsy-confirmed tubulointerstitial nephritis and allergic nephritis have been infrequently observed following treatment with Nivolumab. Most cases were Grade 2 or 3 and based on creatinine elevation. Subjects with a history of RCC or prior nephrectomy did not appear to be at higher risk. Events were managed with corticosteroids and, in all cases, renal function partially or fully improved. Physicians should monitor creatinine regularly. As creatinine abnormalities are common in subjects with cancer and other comorbidities, it is important that an evaluation/work-up distinguishes between non-drug-related causes (e.g., dehydration, concomitant medications, hypotension, or progression of disease) and a possible drug-related AE as the management can be quite different. The principal treatment for renal AEs

is corticosteroids. Consultation with a sponsor-investigator should be sought for all moderate- and high-grade cases of renal AEs.

6.3.7 Neurologic Adverse Events

Neurologic AEs have been uncommonly observed following treatment with Nivolumab. Neurologic AEs can manifest as central abnormalities (e.g., aseptic meningitis, encephalopathy, or encephalitis) or peripheral sensory/motor neuropathies (e.g., Guillain-Barre Syndrome, myasthenia gravis complicated with sepsis and fatality). Early recognition and treatment of neurologic AEs is critical to its management. Subjects should be advised to seek medical evaluation if they notice impairment in motor function (e.g., weakness), changes in sensation (e.g., numbness), or symptoms suggestive of possible central nervous system abnormalities such as new headache or mental status changes. As neurologic symptoms can be common in subjects with cancer, it is important that an evaluation/work-up distinguishes between non-drug-related causes (e.g., progression of disease, concomitant medications, or infection) and a possible drug-related AE as the management can be quite different. The principal treatments for neurologic toxicity are dose delay, corticosteroids, and IV immunoglobulin. For high-grade related neurological AEs, Nivolumab should be discontinued. Consultation with a sponsor-investigator should be sought for all moderate and high-grade cases of neurologic AEs.

6.3.8 Infusion Reactions

Infusion reactions, including high-grade hypersensitivity reactions, following administration of Nivolumab are uncommon. Investigators are advised to monitor for fever, chills, shakes, itching, rash, hypertension or hypotension, or difficulty in breathing during and immediately after administration of Nivolumab.

6.3.9 Lipase/Amylase Elevations

Asymptomatic elevations in lipase and amylase have been reported. As lipase/amylase abnormalities are not uncommon in subjects with cancer, it is important that an evaluation/work-up distinguishes between non-drug-related causes (e.g., progression of disease, concomitant medications, or alcohol) and a possible drug-related cause as the management can be quite different. The recommended management of Nivolumab-related elevated lipase/amylase values centers around close observation. Physicians should ensure that subjects have no associated symptoms consistent with pancreatitis, such as abdominal pain. Corticosteroids do not seem to alter the natural history of lipase/amylase elevations. Laboratory values tend to fluctuate on a day-to-day basis and eventually return to baseline or low grade over the course of weeks, whether or not subjects receive corticosteroids. Asymptomatic elevations should be monitored approximately on a weekly basis, and Nivolumab should be held per protocol instructions. For sustained asymptomatic Grade 4 elevations, Nivolumab should be discontinued per protocol instructions. For subjects with elevated lipase/amylase and symptoms consistent with possible pancreatitis, Nivolumab should be discontinued, and consultation with a gastroenterologist should be considered. Consultation with a sponsor-investigator should be sought for all high-grade cases of elevated lipase/amylase.

6.3.10 Uveitis and Visual Complaints

Immune therapies have been uncommonly associated with visual complaints. Inflammation of components within the eye (e.g., uveitis) is an uncommon, but clinically important, event. An ophthalmologist should evaluate visual complaints with examination of the conjunctiva, anterior and posterior chambers, and retina. Topical corticosteroids may be used to manage low-grade events. Low-grade events that do not resolve and high-grade events should be managed with systemic corticosteroids. Consultation with the sponsor-investigator should be sought for all cases of ocular inflammatory events. Complaints of double vision should also prompt medical evaluation. In addition to ocular inflammatory events, a work-up should also consider pituitary inflammation as a cause. Vogt-Koyanagi-Harada syndrome (VKH) is a T-cell mediated autoimmune attack on melanocytes. VKH manifests as a multi-system disorder characterized by granulomatous panuveitis with exudative retinal detachments, often associated with neurologic and cutaneous manifestations. Rare cases have been observed. Based on the severity of the adverse reaction, Nivolumab should be withheld or discontinued, and corticosteroids administered accordingly.

6.3.11 Other Immune-mediated Adverse Events

For suspected immune-related adverse reactions, adequate evaluation should be performed to confirm etiology or exclude other causes. Based on the severity of the adverse reaction, Nivolumab should be withheld or discontinued, and corticosteroids administered accordingly. Upon improvement, Nivolumab may be resumed after corticosteroid taper. If there is recurrence of any Grade 3 or 4 immune-related adverse reactions or life-threatening immune-related adverse reactions, Nivolumab must be permanently discontinued. Rare cases of myotoxicity (myositis, myocarditis, and rhabdomyolysis), some with fatal outcome, have been reported with Nivolumab. If a patient develops signs and symptoms of myotoxicity, close monitoring should be implemented, and the patient referred to a specialist for assessment and treatment without delay. Based on the severity of myotoxicity, Nivolumab should be withheld or discontinued, and appropriate treatment instituted. For grade 3 myocarditis, Nivolumab should be permanently discontinued.

6.3.12 Criteria to Resume Nivolumab Dosing

Participants may resume treatment with study treatment when the drug-related AE(s) resolve to Grade \leq 1 or baseline value, with the following exceptions:

- Participants may resume treatment in the presence of Grade 2 fatigue
- Participants who have not experienced a Grade 3 drug-related skin AE may resume treatment in the presence of Grade 2 skin toxicity
- For participants with Grade 2 AST, ALT and/or Total Bilirubin Abnormalities, dosing may resume when laboratory values return to baseline and management with corticosteroids, if needed, is complete.
- Drug-related pulmonary toxicity, diarrhea or colitis must have resolved to baseline before treatment is resumed. Participants with persistent Grade 1 pneumonitis after completion of a steroid taper over at least 1 month may be eligible for retreatment if discussed with and approved by the site sponsor-investigator

Participants with drug-related endocrinopathies adequately controlled with only physiologic hormone replacement may resume treatment after consultation with the sponsor-investigator. Adrenal insufficiency requires discontinuation regardless of control with hormone replacement.

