6.3 Nivolumab

There will be no dose escalations or reductions of nivolumab allowed. Premedications are not recommended for the first dose of nivolumab. Participants should be carefully monitored for infusion reactions during nivolumab administration. Doses of nivolumab may be interrupted, delayed, or discontinued depending on how well the participant tolerates the treatment. Guidelines on the recommended management are provided in the Investigator Brochure.

Nivolumab administration should be delayed for the following:

- Given hepatic involvement as an inclusion criteria, continue, withhold or permanently discontinue nivolumab based on the severity of hepatitis and baseline AST and ALT levels (following guidelines for use of nivolumab in HCC liver disease):
 - If AST/ALT is within normal limits at baseline and increases to > 3-5x the ULN, withhold dose
 - If AST/ALT is > 1-3x ULN at baseline and increases to > 5-8x the ULN, withhold dose
 - If AST/ALT is > 3-5x ULN at baseline and increases to > 8x the ULN, withhold dose
- Grade 2 non-skin, drug-related AE, with the exception of fatigue
- Grade 2 drug-related creatinine abnormalities
- Grade 3 skin, drug-related AE
- Grade 3 drug-related laboratory abnormality, with the following exceptions:
 - Grade 3 lymphopenia or asymptomatic amylase or lipase does not require dose delay

- Any adverse event, laboratory abnormality, or intercurrent illness which, in the judgment of the investigator, warrants delaying the dose of study medication.

Participants who require delay of nivolumab should be re-evaluated weekly or more frequently if clinically indicated and resume nivolumab dosing when re-treatment criteria are met. In general, in the event of a grade 2 AE, treatment with nivolumab can be resumed when the AE has resolved to \leq grade 1.

Nivolumab treatment should be permanently discontinued for the following:

- If AST/ALT increases to $> 10x$ the ULN or total bilirubin increases to $> 3x$ ULN, permanently discontinue (following guidelines for use of nivolumab in HCC liver disease).
- Any Grade 2 drug-related uveitis, eye pain or blurred vision that does not respond to topical therapy and does not improve to Grade 1 severity within the re-treatment period OR requires systemic treatment

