- Any Grade 3 non-skin, drug-related AE lasting > 7 days or recurs, with the following exceptions for laboratory abnormalities, drug-related uveitis, pneumonitis, bronchospasm, neurologic toxicity, hypersensitivity reactions, infusion reactions, and endocrinopathies:
 - Grade 3 drug-related uveitis, pneumonitis, bronchospasm, neurologic toxicity, hypersensitivity reaction, or infusion reaction of any duration requires discontinuation
 - Grade 3 drug-related endocrinopathies, adequately controlled with only physiologic hormone replacement do not require discontinuation. Adrenal insufficiency requires discontinuation regardless of control with hormone replacement.
 - Grade 3 drug-related laboratory abnormalities do not require treatment discontinuation except:
 - Grade 3 drug-related thrombocytopenia > 7 days or associated with bleeding requires discontinuation

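### Section 6.3.12 ties the return-to-baseline liver restart target to Grade 2 only, so at normal baseline a delayed Grade 3 AST/ALT rise gets a looser laboratory target; separately, the 6.3 and Appendix 1 stopping limits conflict

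*Combined protocol and SAP*

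**What the plan says.** - **Default restart rule (6.3.12).** "Participants may resume treatment with study treatment when the drug-related AE(s) resolve to Grade" 1 or lower, or to the baseline value, subject to listed exceptions.
- **Liver exception (6.3.12).** "For participants with Grade 2 AST, ALT and/or Total Bilirubin Abnormalities, dosing may resume when laboratory values return to baseline", and any corticosteroid treatment that was needed must be finished. No exception names Grade 3 AST/ALT.
- **Delay (6.3).** AST/ALT withholding depends on baseline. With normal baseline the row is a rise to >3-5x ULN, and with baseline >1-3x it is a rise to >5-8x. The third row reads "If AST/ALT is > 3-5x ULN at baseline and increases to > 8x the ULN, withhold dose". The general list also delays for "Grade 3 drug-related laboratory abnormality, with the following exceptions". Those exceptions are lymphopenia and asymptomatic amylase or lipase; AST/ALT is not among them.
- **Permanent stop (6.3).** "If AST/ALT increases to $> 10x$ the ULN or total bilirubin increases to $> 3x$ ULN, permanently discontinue". The same section says "Grade 3 drug-related laboratory abnormalities do not require treatment discontinuation except" for thrombocytopenia that lasts more than 7 days or comes with bleeding. Laboratory abnormalities are also excepted from the rule that stops nivolumab for a long or recurrent Grade 3 event.
- **Appendix 1, hepatic algorithm.** A footnote permits delay instead of discontinuation when AST/ALT is at most 8x ULN and total bilirubin at most 5x ULN. The figure it belongs to is not visible in the text available here.

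**The concern.** A restart rule should be at least as cautious after a worse event as after a milder one. Read literally, 6.3.12 does the reverse for AST/ALT at normal baseline: Grade 2 must return to baseline, while a delayed Grade 3 need only reach Grade 1. Every participant has liver metastases, and section 6.1 lists transaminitis among the mFOLFOX6 toxicities, so AST/ALT rises are a foreseeable reason to hold nivolumab.

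The second problem stands on its own. Two parts of the protocol give different limits for stopping nivolumab for good, and sites in a multi-centre trial could follow either. What is at stake is consistent and cautious re-dosing, not the efficacy comparison.

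**Working it through.** The main check is textual. The small amount of arithmetic only sizes the gap.

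**Inputs.** The rows, limits and restart rules come from 6.3, 6.3.12 and the Appendix 1 footnote. Three values are assumed because the documents do not print the CTCAE v4 AST/ALT cut-offs: Grade 1 ceiling 2-3x ULN, Grade 2/3 boundary 5x ULN, and normal baseline at most 1x ULN.

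**1. Two patients with normal baseline AST/ALT**

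| | Peak 4x ULN | Peak 7x ULN |
|---|---|---|
| Grade (assumed boundary 5x) | 2 | 3 |
| Withheld by | normal-baseline row (>3-5x) | general Grade 3 laboratory rule; the row ends at 5x |
| Permanent stop under 6.3 | no (4 < 10) | no (7 < 10) |
| 6.3.12 rule that applies | liver exception | default |
| Highest value at restart | about 1x | 2-3x |

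The example works for any Grade 2/3 boundary between 4x and 7x.

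**2. Size of the gap.** The restart ceiling after Grade 2 is the baseline B. After a delayed Grade 3 it is the higher of the Grade 1 ceiling G and B. So gap = max(G, B) - B.

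- B = 1x and G = 2, 2.5 or 3x: gap = 1, 1.5 or 2x ULN.
- B = 4x or 5x: gap = 0, because the default already amounts to baseline.

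**3. Affected peaks.** From the 5x boundary to the stopping limit: 10 - 5 = 5x ULN wide under 6.3, or 8 - 5 = 3x ULN wide under the footnote.

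**4. Stopping limits (no CTCAE assumption needed)**

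- Bilirubin 4x, AST/ALT 7x: 6.3 stops permanently (4 > 3). The footnote permits delay (4 ≤ 5 and 7 ≤ 8).
- AST/ALT 9x, bilirubin 2x: 6.3 does not force a stop (9 < 10 and 2 < 3). The footnote's permission to delay does not reach this patient (9 > 8).
- Third row of 6.3 (withhold above 8x): with a 10x stop, the withholding range is 10 - 8 = 2x ULN. With an 8x stop it is 8 - 8 = 0.

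**5. When nivolumab is given (5.1.2, 5.1.4, 5.1.5).** Planned doses are 4 + 8 + 24 = 36 in Arm A and 2 + 4 + 8 + 24 = 38 in Arm B.

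- Before surgery: 4/36 = 11.1% and 6/38 = 15.8%.
- With mFOLFOX6: 12/36 = 33.3% and 12/38 = 31.6%.

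These fractions describe timing and overlap with chemotherapy. They do not estimate how often the problem would arise.

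**The case against.** **The route to a delayed Grade 3 is partly inferred.** For normal baseline the specific row in 6.3 ends at 5x ULN and no row covers >5-10x. Placing that band under the general Grade 3 laboratory rules is the natural reading, but the section does not state it. This stands, and the fix should settle whether such a patient is withheld or stopped.

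**Grade 2 may mean the grade at restart.** A patient coming down from Grade 3 passes through Grade 2 and would then be held to baseline, which removes the inversion. The neighbouring fatigue bullet concerns the grade present at restart. Against this, the skin bullet also looks at grade history, and there the worse event gets the stricter rule. Section 6.3.12 does not decide the matter.

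**Guidance may sit elsewhere.** The Appendix 1 hepatic figure is not visible, and 6.3 refers to the Investigator Brochure for management. A reader might infer that the plan has no Grade 3 hepatic restart level at all. The documents do not support that; the point is limited to what 6.3.12 and 6.3 print.

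**Corticosteroids.** A reader might infer that a Grade 3 patient could restart while still on corticosteroids, because the completion condition sits in the Grade 2 bullet. Section 6.3.11 largely covers this: for suspected immune-related reactions, nivolumab resumes only after a taper, with no grade limit. No contrast on corticosteroids is claimed.

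**Other safeguards.** The restart wording is permissive. Section 6.3 asks for at least weekly re-evaluation during a delay and lets the investigator delay for any laboratory abnormality. Section 6.3.3 says "Physicians should monitor LFTs prior to each Nivolumab treatment" and advises consultation for moderate- and high-grade hepatic events. Section 6.3.11 adds: "If there is recurrence of any Grade 3 or 4 immune-related adverse reactions", nivolumab must be stopped permanently. These limit the harm, but none gives a laboratory restart level.

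**Conclusion.** The point holds as a minor safety inconsistency in two parts.

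**Restart target.** On the printed text, a normal-baseline patient whose Grade 3 AST/ALT rise was delayed has a looser laboratory target than one whose rise was Grade 2. The gap is 1-2x ULN under the assumed cut-offs. The direction follows from the grades alone and needs only that Grade 1 lies above a normal baseline. It also depends on the general Grade 3 rules covering the >5-10x band, on Grade 2 not meaning the grade at restart, and on the unseen figure not saying otherwise. Confidence is medium for these reasons.

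**Stopping limits.** The conflict over bilirubin (3x against 5x) and AST/ALT (10x against 8x) is visible in the printed text. Which branch of the figure the footnote qualifies is unknown.

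Two wider readings are not supported. A reader might extend the inversion to bilirubin or to raised baselines. But bilirubin above 3x is already a permanent stop in 6.3, at baseline >3-5x the gap is zero, and no claim is made for baseline >1-3x. A reader might also infer harm to the resection or to the survival comparison. Most planned nivolumab doses come after surgery (32 of 36 in Arm A, 32 of 38 in Arm B), no event frequency is given, and the primary analysis does not depend on this rule.

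**What to change.** 1. **Restart rule.** Reword the 6.3.12 liver bullet to apply to participants whose highest grade was Grade 2 for AST, ALT or total bilirubin, or Grade 3 for AST/ALT without permanent discontinuation. Leave the rest of the bullet as it is. Using the highest grade also removes the doubt about grade at restart. In 6.3, state whether normal-baseline AST/ALT of >5-10x ULN is withheld or stopped.
2. **Stopping limits.** State that 6.3 governs over the Appendix 1 footnote. After checking the figure, set the footnote's bilirubin limit to 3x ULN. The AST/ALT limit is a clinical choice for the sponsor: 10x, or the more cautious 8x. Use the same value in both places. If 8x is chosen, rewrite the third row of 6.3, which would otherwise have no withholding range.

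**Cost.** A few lines of text at the next amendment. The downside is that some patients with Grade 3 AST/ALT rises, including rises caused by mFOLFOX6, would restart nivolumab later or not at all. The new wording reaches every baseline, so it may also tighten restart for some patients with baseline >1-3x. Section 6 lets the investigator attribute a toxicity to one agent and hold only that one, which limits this cost, although the AST/ALT rows in 6.3 do not mention attribution.
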